5.2 Index regimen with a lower MAP-target (≥ 55 mmHg)

Noradrenaline therapy (dosage and duration) is given with a target MAP of ≥ 55 mmHg.

- If a patient is not on vasoactive drugs at the moment of randomization, noradrenaline is only started when the MAP is < 55 mmHg. Noradrenaline is titrated in accordance with local protocols until the MAP-target of ≥ 55 mmHg has been reached.
- If a patient is on noradrenaline or other vasoactive drugs, treatment is reduced or discontinued when the MAP is consistently ≥ 55 mmHg.
- If, after an initial treatment period with noradrenaline, the target MAP of ≥ 55 mmHg is maintained without any medical intervention, no active blood pressure lowering medication is required.

Blood pressure is continuously monitored by an intra-arterial catheter which is placed according to clinical routine.

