8.3 Tertiary endpoints *(for definitions, see Appendix A)*

The tertiary endpoints are:

- Days alive and out of ICU (30 days)
- Cardiovascular death at 1 year
- Enzymatic infarct size
- Lactate clearance (mean + area under the curve 0-36 hours)
- Days alive and free of mechanical ventilation (30 days)
- Days alive and free of mechanical circulatory support (30 days)
- Severe renal failure requiring renal replacement therapy (at 30 days, 1 year)
- Renal function (during hospital stay and 1 year)
- Time to peak creatinine (hospital stay)
- Time to renal replacement therapy
- Days alive and free of catecholamine therapy (30 days)
- Vasoactive inotropic score (VIS) (during hospital stay)
- Time to hemodynamic stabilization (hospital stay)
- Blood pressure and heart rate during the first 24 hours
- Hemodynamic parameters (during ICU / CCU admission)
- Arrhythmias during hospital admission
- Major vascular complication during admission (bleed or thrombo embolic event)
- Infection / sepsis during hospital admission
- Myocardial re-infarction within 30 days
- Left ventricular ejection fraction (at day 3, before hospital discharge, and at 1 year)

- Neurological outcome (at 30 days and 1 year)
- Protocol adherence / use of bail-out therapy
- Hospital readmission for cardiac reason within 1 year

The cost-effectiveness endpoints are:

- Health-related quality of life based on the EQ-5D-5L questionnaire at 12 months
- Resource utilization based on iMTA Medical Consumption (iMCQ) and iMTA Productivity Cost Questionnaire (iPCQ) (at 30-day, 3-month, 6-month and 1-year follow-up)

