Number of days that a patient spends alive and out of hospital from randomization to 30 days. Calculated by subtracting days in hospital from 30 days for every patient that leaves the hospital alive. If a patient deceases during hospital stay, the DAOH is zero. If a patient dies after hospital discharge, the number of days from their

death to 30 days is counted.

Days alive and out of ICU

Number of days that a patient spends alive and out of the ICU from randomization to 30 days. Calculated by subtracting days in ICU from 30 days for every patient that leaves the ICU alive. If a patient deceases during ICU stay, the *days alive and out of ICU* is zero. If a patient dies after ICU discharge, the number of days from their death to 30 days is counted.

Days alive and free of mechanical ventilation

Counted as 30 days minus the amount of days that a patient was mechanically ventilated. These days are counted as the difference between start date of mechanical ventilation and the date of discontinuation. If a patient was ventilated during more than one episode, the total number of days counts. If a patient dies after discontinuation of mechanical ventilation, but before 30 days, the amount of days between their death and 30 days, are also subtracted from 30.

Days alive and free of mechanical circulatory support (MCS)

Counted as 30 days minus the amount of days that a patient received any form of MCS (IABP, Impella, ECMO, LVAD). These days are counted as the difference between start date of mechanical ventilation and the date of discontinuation. If a patient was ventilated during more than one episode, the total number of days counts. If a patient dies after discontinuation of mechanical ventilation, but before 30 days, the amount of days between their death and 30 days, are also subtracted from 30.

Renal function at during hospital stay and at 1 year

Measured by creatinine ($\mu\text{mol/L}$) and expressed as estimated glomerular filtration rate (eGFR).

Time to renal replacement therapy

Time to initiation of renal replacement therapy expressed in days from randomization.

Time to peak creatinine

Time to highest creatinine-level ($\mu\text{mol/L}$) during hospitalization expressed in days from randomization.

Days alive and free of catecholamine therapy

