Counted as 30 days minus the amount of days that a patient received any type of catecholamine. These days are counted as the difference between start date of catecholamine therapy and the date of discontinuation. If a patient received catecholamine therapy during more than one episode, the total number of days counts. If a patient dies after discontinuation of catecholamine therapy, but before 30 days, the amount of days between their death and 30 days, are also subtracted from 30.

Time to hemodynamic stabilization

Earliest time by which the patient is hemodynamically stable and receives no catecholamine therapy, expressed in amount of days, counted from randomization.

Blood pressure and heart rate

As measured by (non-)invasive hemodynamic monitoring, reported hourly.

Hemodynamic parameters

Cardiac index (L/min/m²), pulmonary capillary wedge pressure (mmHg), right atrial pressure (mmHg), pulmonary artery pressure (mmHg) and pulmonary artery pulsatility index every 8 hours during the first 48 hours of admission.

Arrhythmias during admission

Type	Definition
Atrial	Atrial flutter, tachycardia or fibrillation
Ventricular	Monomorphic or polymorphic VT greater than 30 seconds or hemodynamically unstable ventricular arrhythmia requiring intervention, or VF.

Vasoactive inotropic score

Dopamine dose ($\mu\text{g}/\text{kg}/\text{min}$) +
 Dobutamine dose ($\mu\text{g}/\text{kg}/\text{min}$) +
 100 x Epinephrine dose ($\mu\text{g}/\text{kg}/\text{min}$) +
 10 x milrinone dose ($\mu\text{g}/\text{kg}/\text{min}$) +
 10.000 x vasopressin dose (U/kg/min) +
 100 x norepinephrine dose ($\mu\text{g}/\text{kg}/\text{min}$)

Ischemic complication during admission

Type	Definition
Acute limb ischemia	
Rutherford I	Limb viable, not immediately threatened
Rutherford IIa	Limb marginally threatened, salvageable if promptly treated
Rutherford IIb	Limb immediately threatened, salvageable with immediate revascularization
Rutherford III	Limb irreversibly damaged, major tissue loss or permanent nerve damage inevitable
Mesenteric ischemia	As proven by mesenteric angiography, CT angiography, pathology or based on high clinical suspicion. (Suspicion might arise in critically ill patients with abdominal pain or distension requiring vasopressor support and evidence of multi-organ dysfunction.)

Thromboembolic event during admission

Deep venous thrombosis, pulmonary embolism, cerebrovascular event.

Major bleed during admission

Major bleed	

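### Appendix A counts days free of mechanical circulatory support from ventilation dates, so this tertiary endpoint is wrong as written

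*Protocol*

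**What the plan says.** Section 8.3 lists "Days alive and free of mechanical circulatory support (30 days") among the tertiary endpoints and sends the reader to Appendix A for the definition. There the entry begins correctly: "Counted as 30 days minus the amount of days that a patient received any form of MCS (IABP, Impella, ECMO, LVAD"). The switch to another therapy comes where the first sentence meets the second: "received any form of MCS (IABP, Impella, ECMO, LVAD). These days are counted as the difference between start date of mechanical ventilation". The three operative rules that follow are:

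- Counting rule: "These days are counted as the difference between start date of mechanical ventilation and the date of discontinuation".
- Episode rule: "If a patient was ventilated during more than one episode, the total number of days counts".
- Death rule, opening condition: "If a patient dies after discontinuation of mechanical ventilation, but before 30 days", in which case the days from death to day 30 are subtracted as well.

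These rules match those of the ventilation endpoint directly above. The catecholamine entry has the same structure but names its own therapy: "These days are counted as the difference between start date of catecholamine therapy and the date of discontinuation".

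Section 7.1.5 lists the duration of MCS and the duration of mechanical ventilation as separate eCRF items. Table 1 likewise has separate rows for mechanical support and ventilation.

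**The concern.** The first sentence of the MCS definition asks for device days, while the rules that produce the number use ventilation days. The definition therefore contradicts itself. A programmer who follows the rules produces a second copy of ventilator-free days under an MCS label.

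This matters for interpretation because section 5.4 allows devices as bail-out when medical therapy fails, and section 4.4 excludes patients with an imminent need for them. MCS-free days are thus one of the measures that could show whether the lower MAP target leads to more device use. As written, the endpoint cannot show it.

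A smaller matter sits in the same sentences. The ventilation, MCS and catecholamine definitions all take discontinuation date minus start date, summed over episodes, with no clock time and no minimum of one day.

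**Working it through.** The protocol gives no worked figure for these endpoints, so there is none to reproduce. The check applies the Appendix A rules to constructed patients.

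**MCS definition.** All patients below are hypothetical and alive at day 30.

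Rule as written: 30 − (ventilation stop day − ventilation start day).
Rule on MCS dates, same date-difference method: 30 − (MCS removal day − MCS start day).

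| Course | As written | On MCS dates | Error |
|---|---|---|---|
| MCS days 1–5, ventilated days 1–2 | 30 − (2 − 1) = 29 | 30 − (5 − 1) = 26 | +3 |
| MCS days 1–5, never ventilated | 30 − 0 = 30 | 30 − (5 − 1) = 26 | +4 |
| MCS days 1–3, ventilated days 1–6 | 30 − (6 − 1) = 25 | 30 − (3 − 1) = 28 | −3 |

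The error can go either way. It depends on how long the patient was ventilated relative to the time on a device.

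**Date-difference counting (secondary).** Used days under three conventions, for constructed catecholamine courses:

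| Course | Date difference | Elapsed days | Calendar days touched |
|---|---|---|---|
| One course 08:00–20:00 (12 h) | 0 | 12/24 = 0.5 | 1 |
| One course 22:00–02:00 (4 h) | 1 | 4/24 = 0.17 | 2 |
| Three courses 08:00–20:00 on three days (36 h) | 0 | 36/24 = 1.5 | 3 |
| Three courses 22:00–02:00 on successive nights (12 h) | 3 | 12/24 = 0.5 | 4 |

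By date difference, the patient with 36 h of exposure scores 30 free days and the patient with a single 4 h course scores 29. That order is the reverse of true exposure.

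**Does this rule favour one arm?** If start times are uniform over 24 h, a course of h hours, with h below 24, crosses midnight with probability h/24. The expected date difference then equals the elapsed time. For 36 h it is 1 + 12/24 = 1.5. A simulation of 200,000 courses per duration agrees:

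| Duration | Mean date difference | Elapsed days |
|---|---|---|
| 4 h | 0.168 | 0.167 |
| 12 h | 0.501 | 0.500 |
| 20 h | 0.832 | 0.833 |
| 36 h | 1.502 | 1.500 |

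Under that assumption the rule is noisy for the individual patient and unbiased on average.

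**The case against.** The strongest reply on the MCS definition is that its heading and first sentence make the intention plain, that any careful statistician would read MCS for ventilation, and that device use is captured elsewhere (the eCRF items, Table 1, and the separate tertiary endpoint on protocol adherence and bail-out therapy). This is fair, and it limits the severity. It does not remove the error. Section 8.3 points to Appendix A as the place where the endpoint is fixed, and all three operative rules name the wrong therapy.

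On date differences, the reply is that section 9.4 leaves the tertiary analyses to the statistical analysis plan, where same-day handling is often settled, and that the rule is identical in both arms. That also has weight, so this remains a secondary point.

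A reader might go further and infer that the date-difference rule inflates catecholamine-free days in the index arm, because section 5.2 says that "treatment is reduced or discontinued when the MAP is consistently ≥ 55 mmHg" and so might produce many short courses. The documents do not support this:

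- Sections 5.2 and 5.3 give no number, length or timing of courses in either arm. Section 5.2 speaks of reducing as well as stopping.
- The endpoint counts any catecholamine, so pausing noradrenaline does not end the count if another is running.
- Short courses that cross midnight are over-counted: three 4 h night courses cost 3 days against 0.5 elapsed. More short courses could therefore equally penalise an arm.
- A shortfall of one day for each separate course appears only against inclusive calendar-day counting. That is itself a convention and can misorder patients too: in the table above, 12 h at night touches 4 calendar days and 36 h by day touches 3.

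**Conclusion.** The MCS definition is wrong as written. Applied literally, it misstates the constructed patients by 3 or 4 days out of 30, in either direction, and it yields no information on device use. The trial-wide effect cannot be sized, because the protocol gives no expected device or ventilation durations. Severity is minor: the endpoint is tertiary, outside the hierarchy of section 9.2, and the intended meaning can be recovered.

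Secondary: date differences in the ventilation, MCS and catecholamine definitions can misorder individual exposure when courses are short. No direction of bias between arms is shown. The finding of no average bias rests on uniform start times, which is an assumption; the protocol gives nothing that would establish a bias either way.

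**What to change.** In the MCS entry of Appendix A, rewrite the counting, episode and death rules so that each refers to the start and removal of MCS. Sum over devices and episodes, and count overlapping devices once. This costs a wording change and a programming rule. MCS duration is already collected under section 7.1.5, although start and removal dates for each device must be available to handle overlap.

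For the three support-day definitions, state one counting convention for both arms. Where start and stop times are recorded, summing elapsed hours and dividing by 24 avoids the misordering. The cost is that clock times are needed. If only dates exist, say explicitly how a same-date course is scored.

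While these sentences are open, also state how death on support is scored. The death rule covers only death after discontinuation. Read literally, a patient who starts on day 1 and dies on support on day 2 could score 30 − 1 = 29 free days, or 30 − 2 = 28 if both days are counted.

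### Three tertiary support-free-day endpoints take off post-death days only when death follows the end of support, so early deaths on support, or without it, can score near 30.

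*Protocol*

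**What the plan says.** Section 8.3 of the protocol lists the three endpoints as tertiary, each over 30 days, and refers to Appendix A for their definitions. Appendix A builds all three in the same way.

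- **Starting formula.** Catecholamines: "Counted as 30 days minus the amount of days that a patient received any type of catecholamine". Ventilation: "Counted as 30 days minus the amount of days that a patient was mechanically ventilated". MCS: "Counted as 30 days minus the amount of days that a patient received any form of MCS".
- **Length of support.** For catecholamines: "These days are counted as the difference between start date of catecholamine therapy and the date of discontinuation". For ventilation, and again word for word under MCS: "These days are counted as the difference between start date of mechanical ventilation and the date of discontinuation".
- **Death.** The days from death to day 30 are also subtracted, on one condition. For catecholamines it reads "If a patient dies after discontinuation of catecholamine therapy, but before 30 days". For both ventilation and MCS it reads "If a patient dies after discontinuation of mechanical ventilation, but before 30 days".

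None of the three says what to do when a patient dies while still on support, or dies without ever having received it. The definition of days alive and out of hospital (DAOH), in the same appendix, does deal with the parallel case: "If a patient deceases during hospital stay, the DAOH is zero". The definition of days alive and out of ICU likewise gives zero for death in the ICU.

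**The concern.** A count of days alive and free of support should give no credit for days after death. Here the subtraction depends on support having been stopped first. In a trial of cardiogenic shock that condition may often fail: a patient can die with the noradrenaline infusion running or while ventilated, and a patient can die early without ever having had MCS, which section 5.4 allows only as bail-out. Under the literal rule such patients keep most or all of the 30 days. The sooner a patient dies on support, the higher the score.

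At stake is how these endpoints would read beside mortality. If the regimens differ in early deaths, the arm with more of them gains credit for short support, and the comparison of support-free days loses or even reverses the mortality component that its name promises. Separately, two analysts working from the MCS definition could derive different variables from the same records.

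**Working it through.** The protocol gives no figure for this rule, so there is none to reproduce. The check applies the rule to individual patients and then to arm means.

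**Rules compared**

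- Literal: score = 30 − support days, minus (30 − day of death) only if death follows discontinuation. For a patient who dies on support, the end of support is taken as the day of death. This is an assumption, because the text defines no discontinuation date for such a patient.
- All deaths: score = 30 − support days − (30 − day of death) for every death before day 30.

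**Single patients, support from day 0**

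| Patient | Literal | All deaths |
|---|---|---|
| Dies on support, day 1 | 30 − 1 = 29 | 30 − 1 − 29 = 0 |
| Dies on support, day 2 | 30 − 2 = 28 | 30 − 2 − 28 = 0 |
| Dies on support, day 5 | 25 | 0 |
| Dies on support, day 20 | 10 | 0 |
| Support 2 days, stopped, dies day 3 | 30 − 2 − 27 = 1 | 1 |
| Never on this support, dies day 2 | 30 | 30 − 0 − 28 = 2 |
| Survivor, 5 support days | 25 | 25 |
| Survivor, 10 support days | 20 | 20 |

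One day separates the second and fifth patients: same support, death on day 2 still on support or on day 3 after stopping. The literal scores are 28 and 1. Survivors' scores are the same under both rules.

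**Arm means**

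Write S for the survivors' mean score and D for the mean score of those who die. If S and D are equal in the two arms and mortality is 10 percentage points lower in the index arm, the index-minus-reference difference is 0.10 × (S − D). The 10 points are the difference between 45.9% and 35.9% in section 9.3. Those are rates of death or renal replacement therapy, used here only as a stand-in for mortality.

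Illustrative assumptions, not in the protocol: survivors have 5 support days (S = 25); a death on support falls on day 2 (28 literal, 0 under the all-deaths rule); a death after stopping leaves one free day (1 under both).

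- All deaths on support, literal: 0.10 × (25 − 28) = −0.3 days. The arm means are 0.459 × 28 + 0.541 × 25 = 26.4 (reference) and 0.359 × 28 + 0.641 × 25 = 26.1 (index), so the arm with more deaths looks slightly better.
- All deaths on support, all-deaths rule: 0.10 × (25 − 0) = +2.5 days (means 13.5 and 16.0).
- Half of deaths on support, literal: D = 0.5 × 28 + 0.5 × 1 = 14.5, so 0.10 × 10.5 = +1.05 days.
- Half of deaths on support, all-deaths rule: D = 0.5, so 0.10 × 24.5 = +2.45 days.
- No deaths on support: 0.10 × (25 − 1) = +2.4 days under both rules.

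If a share q of deaths is on support, the literal difference is 0.10 × (24 − 27q). It changes sign only when q exceeds 24/27 = 0.89.

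Spreading the times out instead (exponential, mean 3 or 5 days to death and 4 or 5 days to weaning, all deaths on support) gives −0.2 to +0.1 days under the literal rule and +2.5 to +2.6 under the all-deaths rule.

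**MCS definition**

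Take a survivor with 2 days of MCS and 5 days of ventilation. The opening sentence gives 30 − 2 = 28. The sentence on dates gives 30 − 5 = 25. The death condition then turns on the end of ventilation, even if MCS stopped earlier or later.

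**The case against.** Four points can be made on the other side.

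1. *The score of 28 is one reading of a rule that is silent.* If death itself counts as discontinuation, both for the length of support and for the death condition, a patient on support from day 0 until death scores 0. The endpoint names favour that reading. This stands in part: 28 requires taking death as the end of support and then not applying the death sentence. But the text does not say that death is discontinuation, and that reading does not help the patient who was never on support.
2. *These are tertiary endpoints.* They lie outside the four-step hierarchy in section 9.2. Mortality is judged directly in the primary endpoint and the first ranked secondary endpoint, and the data safety monitoring board considers all-cause death under section 9.7. This stands in full. A reader might infer that the flaw could hide excess deaths or touch the main conclusions; it could not.
3. *The SAP may settle it.* Section 9.4 leaves the tertiary analyses to the SAP, but section 8.3 sends the reader to Appendix A for the definitions. They are stated there, and they are faulty as stated.
4. *The size rests on assumptions.* This stands. The protocol gives no times of death or weaning and no share of deaths on support. Putting every death on support gives close to the largest effect, and composite rates overstate mortality. The figures do not carry over to MCS, which many patients may never receive.

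Two stronger readings are tempting. A reader might infer that catecholamine-free days is the trial's main evidence of reduced drug exposure. The protocol does not say so: section 8.3 also lists the vasoactive inotropic score, and section 7.1.5 records duration of catecholamine therapy separately. A reader might also infer that the MCS endpoint measures ventilator days. Its heading and opening sentence specify MCS, so it contradicts itself and does not simply define something else.

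**Conclusion.** The three definitions are wrong as written. Their death rule leaves out death on support and death in patients never on that support. The literal result conflicts with the endpoint names and differs from the treatment of in-hospital and in-ICU death in the same appendix. A death on support on day 2 scores 28 if support is taken to end at death, and an early death without that support scores 30. The MCS definition is internally contradictory on top of this.

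The effect is confined to three tertiary endpoints. With a 10-point mortality difference and all deaths on support, a true difference of roughly 2.5 days shrinks to about 0. With half of deaths on support, in the example above, it shrinks to about 1. An actual reversal needs nearly all deaths to occur early and on support, and even then is only a few tenths of a day. The text should be corrected before the variables are derived, but it does not threaten the trial's main inference.

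**What to change.** In all three Appendix A definitions, replace the conditional death sentence with one rule: for every patient who dies before day 30, subtract the days from death to day 30, whether or not the support was ever given or had been stopped. State that support days run to discontinuation or death, whichever comes first.

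A rule that only sets death on support to zero would not be enough, because a patient never on that support who dies early would still score 30. The rule above covers both cases and leaves survivors' scores unchanged.

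In the MCS definition, replace the references to mechanical ventilation and to being ventilated with MCS in the sentences on dates, repeat episodes and death.

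The cost is wording in three definitions and matching derivations in the SAP. Dates of death and of support are all that is needed, so there are no new data to collect.

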Intervention: Treatment strategy of reduced noradrenaline use, by means of a lower MAP-target regimen (≥ 55 mmHg).

Main study parameters/endpoints: Primary endpoint: composite of all-cause mortality and severe renal failure leading to renal replacement therapy within 30-days after randomization. Secondary endpoints: duration of catecholamine therapy, enzymatic infarct size, hemodynamic parameters, length of stay in hospital and Intensive Care Units (ICU), quality of life (QOL).

Nature and extent of the burden and risks associated with participation, benefit and group relatedness: In this study no new or additional medication is registered to patients when compared to routine care. This means that all potential risks originate from using a lower MAP-target and reduced use of noradrenaline. In both index and reference group, renal and cerebral functions will be closely monitored.

A potential benefit from study participation is that less exposure to noradrenaline leads to less frequent occurrence of side effects, such as (supra-)ventricular arrhythmias.

The follow-up moments are at 30-days, 3-month, 6-month and 1-year after randomization. These are all part of routine care. At follow-up information on organ function (blood test, ECG, echocardiography) will be gathered, as part of routine care. Additionally, patients will be asked to fill in a questionnaire at 30-days, 3-months, 6-months and 1-year after randomization.

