BARC 2	Any overt, actionable sign of hemorrhage (e.g., more bleeding than would be expected for a clinical circumstance, including bleeding found by imaging alone)

	that does not fit the criteria for type 3, 4, or 5 but does meet at least one of the following criteria: 
 • requiring nonsurgical, medical intervention by a health-care professional, • leading to hospitalization or increased level of care, or prompting evaluation
BARC 3	Clinical, laboratory and/or imaging evidence of bleeding with specific healthcare provider responses as listed below:
3a	
 • Overt bleeding plus hemoglobin drop of 3 to < 5 g/dL* (provided hemoglobin drop is related to bleed) • Any transfusion with overt bleeding
3b	
 • Overt bleeding plus hemoglobin drop ≥5 g/dL* (provided hemoglobin drop is related to bleed), • Cardiac tamponade • Bleeding requiring surgical intervention for control (excluding dental/nasal/skin/hemorrhoid) • Bleeding requiring intravenous vasoactive agents
3c	Intracranial hemorrhage (does not include microbleeds or hemorrhagic transformation, does include intraspinal)
BARC 4	CABG-related bleeding 
 • Perioperative intracranial bleeding within 48 h. • Reoperation after closure of sternotomy for the purpose of controlling bleeding • Transfusion of ≥ 5 U whole blood or packed red blood cells within a 48-h period • Chest tube output more than or equal to 2L within a 24-h period
BARC 5	Fatal bleeding
5a	Probable fatal bleeding; no autopsy or imaging confirmation but clinically suspicious
5b	Definite fatal bleeding; overt bleeding or autopsy or imaging confirmation

Infection / sepsis during admission

Culture proven or for which antibiotics have been started because of high suspicion.

Myocardial re-infarction within 30 days

Acute myocardial injury with clinical evidence of acute myocardial ischemia and with detection of a rise and/or fall of cardiac troponin values with at least one value above the 99th percentile upper reference limit and at least one of the following:

- Symptoms of myocardial ischemia
- New ischemic ECG changes
- Development of pathological Q waves
- Imaging evidence of new loss of viable myocardium or new regional wall motion abnormality in a pattern consistent with an ischemic etiology

Identification of a coronary thrombus by angiography or autopsy

Left ventricular ejection fraction

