The fraction of chamber volume ejected in systole (stroke volume) in relation to the volume of the blood in the

ventricle at the end of diastole (end-diastolic volume), measured by echocardiography, magnetic resonance imaging (MRI) or computed tomography (CT).

Neurological outcome, measured by Modified Rankin Scale, at 30 days and 1 year	
Type	Definition
MRS 0	No symptoms
MRS 1	No significant disability. Able to carry out all usual activities, despite some symptoms
MRS 2	Slight disability. Able to look after own affairs without assistance, but unable to carry out all previous activities.
MRS 3	Moderate disability. Requires some help, but able to walk unassisted.
MRS 4	Moderate severe disability. Unable to attend to own bodily needs without assistance, and unable to walk unassisted.
MRS 5	Severe disability. Requires constant nursing care and attention, bedridden, incontinent.
MRS 6	Dead

Protocol adherence

Whether or not cross-over took place for patients who were randomized to the interventional arm.

Hospital readmission for cardiac reason within 1 year

Unscheduled hospital admission (for at least one night after discharge from the initial hospitalization) for a primary cardiac diagnosis with a length of stay that either exceeds 24 hours or crosses a calendar day after discharge from the initial hospitalization.

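### In-hospital stroke has no definition and no endpoint of its own: it is pooled with venous thromboembolism and with bleeds from BARC 2 upward, which dilutes any difference between arms.

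*Protocol*

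**What the plan says.** **Risk statement.** The Summary traces all potential risks to the lower MAP target and reduced noradrenaline, and adds: "In both index and reference group, renal and cerebral functions will be closely monitored".

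**Where stroke is counted.** Appendix A, under thromboembolic event during admission, gives only this list: "Deep venous thrombosis, pulmonary embolism, cerebrovascular event". Sections 7.1.5 and 8.3 carry the group forward as one combined item, "Major vascular complication during admission (bleed or thrombo embolic event").

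**The bleeding half.** The Appendix A table headed as major bleed begins at BARC 2, described as "Any overt, actionable sign of hemorrhage" that meets at least one further condition. The last of these conditions reads "leading to hospitalization or increased level of care, or prompting evaluation". Grade 3c is "Intracranial hemorrhage (does not include microbleeds or hemorrhagic transformation, does include intraspinal").

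**Other neurological measures.** Section 8.3 has a separate tertiary endpoint, "Neurological outcome (at 30 days and 1 year"), which Appendix A defines as "Neurological outcome, measured by Modified Rankin Scale, at 30 days and 1 year". Appendix A also lists stroke among the causes of cardiovascular death, as a category that may be collected. Section 10.2.1 requires all observed or spontaneously reported adverse events to be recorded.

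**The concern.** Stroke is a harm that a lower pressure target could plausibly cause, and the Summary itself singles out cerebral function. Renal harm, the other function named there, is in the primary endpoint and in several tertiary endpoints. Acute cerebral harm has only a share of a mixed item.

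Two problems follow. First, the pooled item contains events with no obvious link to cerebral perfusion, so a rise in stroke would appear as a small relative change. If bleeding or venous thromboembolism moved the other way, it might not appear at all. Second, the event is undefined and sits under a heading that implies a thromboembolic cause, so sites may differ in what they enter.

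Section 9.2 allows the lower target to be declared non-inferior on the primary endpoint. Readers would then look to the tertiary items for harm, and a statement that major vascular complications did not increase could coexist with more strokes.

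**Working it through.** **1. Where each kind of cerebral injury falls in Appendix A**

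| Event | Heading | Comment |
|---|---|---|
| Thromboembolic stroke | Thromboembolic event | Listed with DVT and PE; no definition |
| Intracranial haemorrhage | Major bleed, BARC 3c | Excludes haemorrhagic transformation |
| Injury from hypoperfusion | None clear | The ischaemic complication heading covers only limb and mesenteric ischaemia |
| Stroke before admission | Prior stroke (medical history) | Fully defined by tissue injury, with imaging or lumbar puncture evidence |

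Stroke is thus split across two components of the pooled item, and one mechanism is left without a clear place. A usable definition exists, but only for history.

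**2. What the schedule adds.** Tables 1 and 2 list no neurological assessment during the ICU stay. The first scheduled one is the 30-day score, which section 5.5 places in a telephone contact after discharge; the next is at 1 year. Section 11.1 names adjudication for primary and secondary endpoint events and does not mention tertiary ones, in an open-label trial.

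**3. Size of the dilution.** The protocol states no stroke, thromboembolism or bleeding rate, so there is no figure to reproduce and every rate below is an assumption.

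Inputs: n = 388 per arm (776 randomised, section 9.3); two-sided 5% test; stroke rates s of 3% (reference) and 7% (index); other components independent of stroke, at the same rate b in both arms.

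- Pooled rate in an arm: p = b + (1 − b)s
- Standard error: SE = √{[p0(1 − p0) + p1(1 − p1)]/388}
- Power: Φ((p1 − p0)/SE − 1.96)

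| b | p0 | p1 | Ratio | SE | (p1 − p0)/SE | Power |
|---|---|---|---|---|---|---|
| 0 (stroke alone) | 3.0% | 7.0% | 2.33 | 0.0156 | 2.57 | 73% |
| 10% | 12.7% | 16.3% | 1.28 | 0.0253 | 1.43 | 30% |
| 20% | 22.4% | 25.6% | 1.14 | 0.0306 | 1.04 | 18% |
| 30% | 32.1% | 34.9% | 1.09 | 0.0339 | 0.83 | 13% |

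**4. Sensitivity to the assumed stroke rates.** The same formulas with other pairs give:

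| Stroke rates | Alone | b = 10% | b = 20% | b = 30% |
|---|---|---|---|---|
| 2% vs 4% | 37% | 11% | 8% | 6% |
| 5% vs 10% | 76% | 39% | 25% | 17% |

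The level of power depends on the rates. The loss from pooling appears in every case.

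**5. Offsetting.** Take b = 20% in the reference arm, so p0 = 22.4%. With stroke at 7% in the index arm, the pooled rates are equal if the other events there occur at (0.224 − 0.07)/0.93 = 16.6%. A fall of 3.4 points in the other events would therefore cancel the stroke rise completely. This is conditional arithmetic, not a forecast.

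**The case against.** A reader might infer that cerebral harm would be hidden. The protocol does not support that.

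- The Modified Rankin Scale is a tertiary endpoint in its own right, and a disabling stroke raises the score.
- Fatal stroke counts as death in the primary endpoint and has a cause-of-death category.
- Intracranial haemorrhage has its own BARC code.
- Adverse events are recorded, and an independent DSMB monitors safety.
- Appendix A defines thromboembolic events and bleeds under separate headings, and section 9.4 leaves tertiary analyses to the SAP. The SAP, or the DSMB charter, neither of which is shown, may already tabulate the components.

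A reader might also infer that minor bleeds would dominate the item. No rate in the protocol shows this, and BARC 2 requires an overt, actionable bleed, not just any bleed that is looked into. Nor does the Summary's sentence on cerebral monitoring promise a stroke endpoint; it can be read as describing patient care. Finally, tertiary endpoints lie outside the hierarchical tests of section 9.2, so no formal claim depends on this item.

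All of this stands, and it limits the point. It does not remove it. The Rankin score is late and global, scores death as 6, does not identify stroke, and can be missing when a patient refuses follow-up beyond discharge (section 5.6.2). The death category covers only fatal strokes. Adverse event recording comes with no stated comparison by arm. The combined item and the thromboembolic heading are choices the protocol makes, not matters it leaves open, and a SAP cannot readily repair an event that was collected without a definition.

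**Conclusion.** The point holds in a limited form. In-hospital stroke is not a separate, defined endpoint, and the item that contains it would dilute a difference between arms. Under the assumed rates of 3% and 7% with 388 per arm, power falls from 73% to between 30% and 13%, and the risk ratio from 2.33 to between 1.28 and 1.09. These figures assume independent other components that are equal in both arms; they illustrate the mechanism and do not predict this trial's rates.

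Separating stroke would not make the comparison well powered: at 2% versus 4% it reaches only 37%. The gain is a visible, interpretable estimate. Calling a table that starts at BARC 2 major bleeding is a smaller labelling fault that stands independently. Neither matter touches the primary analysis or the sample size. This is a change that should be made, not a flaw that threatens the trial's main conclusion.

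**What to change.** - **Sections 7.1.5 and 8.3:** list cerebrovascular event during admission as its own tertiary safety endpoint, outside the combined vascular item.
- **Appendix A:** define it with the tissue-injury wording already used for prior stroke. State that it covers ischaemic events, including those from hypoperfusion, and haemorrhagic events. Move it out of the thromboembolic list.
- **Reporting:** give it by arm with its interval, beside separate rows for venous thromboembolism and bleeding.
- **Bleeding item:** either label it BARC 2–5 bleed or report BARC 3–5 separately.

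The cost is endpoint and definition wording and a few extra table rows. The interval for stroke will be wide: with the assumed 3% and 7%, its half-width is 1.96 × 0.0156, about 3 percentage points around a 4-point difference. Whether stroke also appears in the DSMB reports is for the charter, which is not shown; the sponsor should check that it does.
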